#### **4.1.5 Pharmacokinetics (PK) Endpoints:**

HZN-825 and metabolite(s) plasma concentrations.

## **4.2 Study Treatments**

The dose regimen for all subjects will be HZN-825 300 mg twice every day for 52 weeks. Subjects will take 2 HZN-825 150 mg tablets orally in the morning and evening with a meal. Subjects will participate in a Safety Follow-up Visit 4 weeks after the last dose of HZN-825.

The treatment group will be based on randomized treatment in previous HZNP-HZN-825-301 trial and denoted as QD/BID (HZN-825 300mg QD/HZN-825 300mg BID), BID/BID (HZN-825 300mg BID/HZN-825 300mg BID), and PLC/BID (Placebo/HZN-825 300mg BID) accordingly.

### **4.3 Sample Size and Power Considerations**

The sample size is based on the number of subjects who completed Trial HZNP-HZN-825-301.

### **4.4 Interim Analyses**

No interim analyses are planned.

## **5 Study Analysis Sets**

Four analysis sets will be defined for this trial.

### **5.1 Full Analysis Set**

The full analysis set (FAS) will include all subjects who were enrolled (i.e., signed the ICF) and who received at least 1 dose or partial dose of HZN-825 in this extension trial. This will be the analysis set used for efficacy data analyses. Subjects will be analyzed according to the treatment group to which they were randomized in the previous trial and combine them as an “Overall” group as appropriate.

### **5.2 Safety Analysis Set**

The Safety Analysis Set will include all subjects who received at least 1 dose or partial dose of HZN-825 in this extension trial. Subjects in this analysis set will be analyzed according to the group determined by the treatment that the subject received in the previous trial and overall, as needed.

### **5.3 Per Protocol Analysis Set**

The Per-Protocol (PP) analysis set will consist of all subjects in the FAS with no major protocol violations that could jeopardize the integrity of data and analysis interpretation. The major protocol violations will be reviewed and approved by Horizon clinician with Biostatistics team. The PP Analysis Set will be used as needed for supportive analysis of the primary endpoint. Subjects in this analysis set will be analyzed according to the treatment group to which they were randomized in the previous trial, and Overall group as needed.

### **5.4 Pharmacokinetic Analysis Set**

The Pharmacokinetic (PK) Analysis Set will include all subjects who received at least 1 dose or partial dose of HZN-825 and had at least 1 PK sample post HZN-825 treatment in this extension trial.

## 6 General Considerations

SAS version 9.4 or higher will be used to perform all data analyses.

Summaries of continuous variables will be in terms of the number of observations, mean, standard deviation, median, first quartile (Q1), third quartile (Q3), minimum and maximum. Other descriptive statistics (e.g. standard error, coefficient of variation) may be reported when appropriate. Categorical variables will be summarized using frequency counts and percentages. Analyses that use other descriptive statistics will have the specific descriptive statistics identified with the analysis in the applicable SAP section. All confidence intervals, statistical tests, and P-values will be reported at 2-sided 5% significance level unless otherwise specified.

## 7 Data Handling

All analyses will be based on observed data. There will be no imputations for missing data except for exploratory purposes as needed.

### 7.1 Study Day

Study day will be calculated as (date of interest – trial drug start date) + 1 if the date of interest occurs on or after the trial drug start date. If the date of interest occurs before the trial drug start date, then the study day will be calculated as (date of interest – trial drug start date). There will be no study day zero.

There are two types of treatment periods, durations, and time-to-event data.

### 7.2 Durations and Time to Event Data

Durations are calculated in days as:

- event end date – event start date + 1, if end time or start time not available.
- event end date/time – event start date/time, if both end time and start time available.

Thus, there will be no duration of 0 if end time or start time are not available. If an event has missing or partially missing start or end date, no duration will be calculated.

For elapsed time (e.g. the time to event), use:

- event date/time – reference date/time, (if time available).

Thus, an event which happens on the same date as the reference date will have an elapsed time of 0, if event time or reference time are not available.

### 7.3 Baseline Definition

Unless otherwise specified, Baseline is defined as the last non-missing observation prior to the first dose of trial drug at the baseline visit as specified. For observations occurring on the same date as the first dose of trial drug where time is not collected but the protocol specifies the evaluation must occur prior to administration of trial drug, the result occurring on the day of first trial drug administration will be considered as Baseline.

Two types of Baselines are defined as below:

- Trial Baseline, defined as the latest non-missing measurement prior to the first dose of HZN-825 (BID) in this HZNP-HZN-825-302 extension trial.
- HZN-825 Baseline, defined as the latest non-missing measurement prior to the first dose of trial drug (QD, BID, Placebo) in HZN-825-301.

### 7.4 Visit Window

For the endpoints that present visit-based data, the variables will be summarized based on the scheduled visits with derived analysis visit windows as needed. No visit windows will be derived for the screening period. For the visits on and after the 1st dose date, the actual visit date will be mapped to the derived analysis visit windows based on the study day.

The visit window details will be in the TFL shells document.

Visit windows have been constructed so that every observation (unscheduled visits included) collected can be allocated to a specific visit. The actual assessment day will be mapped to the windows defined for each scheduled study visit with following rules:

- If more than 1 assessment falls within a visit window, the closest non-missing valid assessment to the scheduled day will be used in the analysis.
- If 2 non-missing assessment actual dates are equidistant from the target study day, the later visit will be used in the analysis.
- For retest values of laboratory and spirometry data, the retest value (the last valid observation assessed corresponding to the same visit) will be chosen.

## 8 Study Population

### 8.1 Subject Disposition

The following summaries will be provided by treatment groups that were randomized in previous trial HZNP-HZN-825-301:

Subject disposition presenting the number and percentages of:

- subjects who were eligible for the HZNP-HZN-825-302 trial
- subjects who received trial drug from the HZNP-HZN-825-302 Trial
- subjects who completed the HZNP-HZN-825-302 Trial
- Subjects who prematurely discontinues trial drug and the reasons.

The number of subjects who were eligible for HZNP-HZN-825-302 will be the denominator for calculation of the percentages for the disposition items above. For all other disposition percentages, including the analysis sets below, the number of subjects who received at least one dose of trial drug will be used as the denominator for the calculation.

Number and percentage of subjects in the analysis sets:

- Full Analysis Set (FAS): It consists of all subjects who were enrolled (i.e., signed the informed consent form) and who received at least 1 dose or partial dose of HZN-825 in this extension trial. Subjects will be analyzed according to the treatment group to which they were randomized in the previous trial.
- Safety Analysis Set: It consists of all subjects who receive at least 1 dose or partial dose of HZN-825 in this extension trial. This analysis set will be analyzed according to the group determined by the treatment that the subject received in the previous trial and overall.
- PP Analysis Set: It consists of all subjects in the FAS with no major protocol violations. The PP Analysis Set will be used as needed for supportive analysis of the primary endpoint.
- PK Analysis Set: It includes all subjects who receive at least 1 dose of HZN-825 and have at least 1 PK sample post dose in this study.

Duration (week) of subjects in study will be summarized for subjects in the FAS by treatment group and overall. Duration of subjects in study will be calculated from Day 1 to the end of study date, on which the end of study assessment is performed. For Trial Baseline, treatment periods will start from the first dose day of HZNP-HZN-825-302 to the end of HZNP-HZN-825-302 trial drug day; for HZN-825 Baseline, treatment periods will start from the first dose

day at trial drug at HZNP-HZN-825-301 to the end of HZNP-HZN-825-302 trial drug day. The number (percent) of subjects with results for each scheduled visit will also be presented.

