## 7.2 Rationale for this Trial

[figure not shown]
Fipaxalparant (HZN-825) is under investigation as a novel therapy for SSc because it selectively antagonizes LPAR1, which has been shown to be associated with skin, pulmonary, cardiac, peritoneal and tubulointerstitial fibrosis, and may be a new therapeutic target for treating fibrotic diseases, including SSc. Details are provided in the current version of the Investigator's Brochure.

This trial is designed as an open-label extension of HZNP-HZN-825-301, in which subjects received fipaxalparant (HZN-825) 300 mg QD, fipaxalparant (HZN-825) 300 mg BID or placebo during the 52-week double-blind Treatment Period. Subjects in this extension trial will receive open-label fipaxalparant (HZN-825) 300 mg BID. This extension trial will allow subjects to have up to 24 months of treatment with fipaxalparant (HZN-825), as well as limit the duration subjects are exposed to placebo. This trial will allow examination of long-term safety and tolerability of fipaxalparant (HZN-825), assessment of the durability of response and/or improved response in subjects who received fipaxalparant (HZN-825) in HZNP-HZN-825-301 and evaluation of efficacy in subjects who received placebo in HZNP-HZN-825-301.

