### **9.3 Selection of Trial Population**

#### **9.3.1 Inclusion Criteria**

Eligible subjects must meet/provide **all** of the following criteria:

1. Written informed consent.
2. Completed the double-blind Treatment Period (Week 52) in Trial HZNP-HZN-825-301; subjects prematurely discontinued from trial drug in Trial HZNP-HZN-825-301 for reasons other than safety or toxicity can be included at the discretion of the Investigator after completing Trial HZNP-HZN-825-301 scheduled visits, including Week 52 assessments.
3. Willing and able to comply with the prescribed treatment protocol and evaluations for the duration of the trial.

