## **10.3 Adverse Events**

### **10.3.1 Treatment-Emergent Adverse Events.**

Treatment-emergent adverse events (TEAEs) are defined as any AEs with an onset date on or after the trial drug start date and time (if known) and no later than 28 days after permanent discontinuation of trial drug.

Refer to the table, listing, and figure shell document for determination of TEAE status in adverse events that are missing critical AE date start and stop information. All TEAEs will be evaluated for both treatment periods (start from first dose at HZNP-HZN-825-301 and HZNP-HZN-825-302 to the end of HZNP-HZN-825-302). Imputed dates are only used for classification of TEAEs.

Prior AEs are defined as any AE with a start date prior to the date of first dose of study treatment. Prior AEs will not be summarized, but will be included in listings.

Follow-up AEs are defined as any AE occurring > 28 days after permanent discontinuation of trial drug for subjects who prematurely discontinue the study medication prior to 52 weeks (i.e. 392 days after first trial drug intake). Follow-up AEs will be identified in the listings as such. Related SAEs will be followed up until resolved or until the event stabilizes and the overall clinical outcome has been ascertained.

The Verbatim terms in the eCRFs will be mapped to preferred terms (PTs) and system organ classes (SOCs) using the current version of MedDRA. Adverse events will be graded for

severity using the Rheumatology Common Toxicity Criteria (RCTC) v2.0 [[Woodworth et al., 2007](#)].

For summaries by SOC, PT, and maximum severity, a subject will only be counted once for each SOC based on the maximum severity level reported for that SOC and once for each unique PT within that SOC level at the maximum intensity level reported for that PT.

For summaries by SOC and PT only, a subject will be counted at most once at the SOC level and at most once at each unique PT within the SOC level. Summaries presenting the frequency of TEAEs by SOC and PT will be ordered alphabetically by SOC and then, within a SOC, alphabetically by PT.

Event Adjusted Incidence Rate (EAIR) is defined as number of subjects with events / total subject-years. Subject-years for each subject will be calculated as (date of first event occurred – first dose date +1)/365.25. For subjects without an event, subject-years for each subject = (last day in study – first dose date +1)/365.25.

EAIR will be summarized by SOC and PT as needed for TEAE.

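### The cumulative TEAE period runs unbroken from first 301 dose to last 302 dose, so untreated months in subjects who stopped 301 drug early count as treatment-emergent time

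*SAP*

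**What the plan says.** Inclusion criterion 2 (Protocol 9.3.1) states that "subjects prematurely discontinued from trial drug in Trial HZNP-HZN-825-301 for reasons other than safety or toxicity can be included", at the investigator's discretion, once the 301 visits through Week 52 are complete. Such a subject is off trial drug from the 301 stop until 302 Day 1.

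SAP 8.1 defines two treatment periods. The one tied to the HZN-825 Baseline starts at the first dose "day at trial drug at HZNP-HZN-825-301 to the end of HZNP-HZN-825-302 trial drug day". SAP 10.3.1 carries this into the adverse event analysis: "All TEAEs will be evaluated for both treatment periods (start from first dose at HZNP-HZN-825-301 and HZNP-HZN-825-302 to the end of HZNP-HZN-825-302". The same section sets the outer limit of treatment emergence at "no later than 28 days after permanent discontinuation of trial drug". For a subject without an event, its EAIR denominator runs from first dose to last day in study.

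SAP 10.3.3.2 takes post-baseline liver values up to 28 days after the last dose. It evaluates them separately from each Baseline to the end of 302, as needed. Protocol 9.6.4 instead asks for adverse event rates per patient-year of follow-up during dosing.

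On grouping, SAP 4.2 says "The treatment group will be based on randomized treatment in previous HZNP-HZN-825-301 trial". The design description in SAP section 4 does not mention subjects who stopped 301 drug early.

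**The concern.** The rules are written as if every subject moved from 301 drug to 302 drug without a break. That is true of a subject still on drug at 301 Week 52, because that visit is 302 Day 1. It is not true of the subjects whom inclusion criterion 2 admits after an early stop. They may have months without trial drug inside what the SAP calls a treatment period.

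What is at stake is attribution in the cumulative displays. An event or a raised transaminase several months after the 301 stop would be tabulated with events on drug, and the untreated time would enter the denominator. Attribution matters for this product, because Protocol 7.1.3.5 lists transaminase increase as an important identified risk. The exposure summary in SAP 10.1 refers to 302 exposure, so it would not show a reader that the gap exists.

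**Working it through.** The documents give no figure to reproduce: no sample size, no count of early stoppers and no stop dates. The check is therefore a reading of the rules followed by person-time arithmetic on labelled assumptions.

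**Which reading of the 28-day limit applies?** If the 301 stop were the permanent discontinuation, nearly all 302 events in these subjects would fall outside the cumulative TEAE window. That would defeat the display and is a strained reading, since a subject who restarts has not stopped permanently. If the limit attaches to the 302 stop, the whole 301 gap lies inside the window. Followed as written, the second reading applies, and untreated days well beyond 28 days after dosing ended count as treatment-emergent. That contradicts the purpose of the limit.

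**Per-subject size.** Inputs from the documents: 52 weeks in 301 (Protocol 7.2), 52 weeks in 302 (Protocol 9.4.1) and a 28-day tail (SAP 10.3.1). The cumulative period is 104 × 7 = 728 days. The stop week s is an assumption.

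- Gap = (52 − s) × 7 days
- Misclassified days = gap − 28
- Share = (gap − 28) / 728

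| Assumed 301 stop | Gap (days) | Beyond 28 days | Share of 728 days |
|---|---|---|---|
| Week 12 | 40 × 7 = 280 | 252 | 34.6% |
| Week 26 | 26 × 7 = 182 | 154 | 21.2% |
| Week 40 | 12 × 7 = 84 | 56 | 7.7% |

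A stop at Week 48 leaves exactly 28 days, so nothing is misclassified.

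**EAIR denominator.** Assume a stop at 301 Week 13, full 302 treatment, a 4-week follow-up and no event.

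- SAP formula from the first 301 dose: (52 + 52 + 4) × 7 = 756 days, or 2.07 years.
- On-drug time plus 28 days after each stop: (13 + 4 + 52 + 4) × 7 = 511 days, or 1.40 years.
- On-drug time only: (13 + 52) × 7 = 455 days, or 1.25 years.

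**Group-level size.** If a fraction f of a group stopped at Week s, gap time as a share of the group's cumulative time is w = f × (52 − s)/104, without deducting the 28-day tail. Both f and s are assumed.

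- f = 5%, Week 39: 0.05 × 13/104 = 0.6%.
- f = 30%, Week 4: 0.30 × 48/104 = 13.8%.

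If the off-drug event rate is q times the on-drug rate, the cumulative rate is 1 − w(1 − q) times the on-drug rate. With q = 0.5:

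- f = 10%, Week 26: 1 − 0.025 × 0.5 = 0.988, about 1% lower.
- f = 20%, Week 13: 1 − 0.075 × 0.5 = 0.963, about 4% lower.

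With q = 1 nothing changes, and with q above 1 the cumulative rate rises. The documents give no value for q.

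**The case against.** The strongest reply is that the main safety analysis is untouched. The primary safety objective runs from 302 Day 1 to 4 weeks after last dose, and Protocol 9.5.3.1.2 starts TEAE reporting at the first 302 dose. The 301 gap enters only the additional cumulative analyses, and the SAP qualifies the cumulative liver evaluation and the EAIR as needed. This stands, so a reader should not infer that the primary safety results are contaminated. The cumulative TEAE evaluation carries no such qualifier.

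Second, the cumulative period starts at the first 301 trial drug, which includes placebo. It may be an observation period across two trials and not a claim of continuous active exposure. This stands in part: for PLC/BID the first year is placebo by design. But the SAP names the span a treatment period and assigns treatment emergence by it, so a break in trial drug still needs a rule.

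Third, the follow-up adverse event definition is framed around one 52-week trial. Applied trial by trial, it would already place late 301 events outside treatment. That is reasonable, but the SAP does not say it.

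Two stronger inferences are not supported. One is that untreated time dilutes the rates: events in the gap are counted too, and nothing in the documents fixes a direction. The other is that the QD/BID and BID/BID FVC results are wrong because Protocol 7.2 seeks "assessment of the durability of response and/or improved response in subjects who received fipaxalparant (HZN-825) in HZNP-HZN-825-301". For early stoppers the change from Trial Baseline is indeed a restart from an off-drug value. Grouping by 301 randomization is nevertheless an explicit choice, consistent across both documents, in an analysis declared descriptive. Protocol 7.2 does not require continuous treatment.

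**Conclusion.** The point holds for the cumulative (HZN-825 Baseline) TEAE display, and for the cumulative liver and EAIR displays if they are produced. There, events, values and person-time more than 28 days after an early 301 stop count as treatment-emergent or on-treatment, contrary to the SAP's 28-day limit and to the dosing-time basis in Protocol 9.6.4. It does not reach analyses from 302 Day 1.

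The share is large for an affected subject who stopped early: 34.6% of the period for an assumed stop at Week 12, falling to 7.7% at Week 40. At group level it is probably modest. The 0.6% to 13.8% range for time and the 1% to 4% change in rate rest entirely on assumed fractions, stop weeks and an assumed off-drug rate. The actual number of subjects and gap lengths are unknown from the documents. This is a gap in specification that is worth closing before database lock.

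**What to change.** In SAP 8.1 and 10.3.1, define the cumulative treatment period as two segments: 301 first dose to 301 last dose + 28 days, and 302 first dose to 302 last dose + 28 days, merged where they touch. Classify TEAEs and compute person-time on these segments, and apply the same rule to the cumulative liver display.

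Tabulate events and liver abnormalities in the gap separately as off-treatment. They should not be dropped, because a late transaminase rise must stay visible.

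Report by group the number of subjects with more than 28 days between last 301 dose and 302 Day 1, and the length of the gap. FVC change from Trial Baseline in QD/BID and BID/BID without these subjects is an optional supportive display. It selects on behaviour after randomization and does not correct the primary analysis.

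The cost is SAP wording, one flag derived from 301 dosing dates and a little more programming, with no new data collection. The downside is slightly fewer events and less person-time in the cumulative on-treatment display.

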## **8.2 Protocol Deviations**

Protocol deviations (PDs) occurring after subjects entered the trial are documented during routine monitoring. The PDs are reviewed and categorized as major and minor prior to the database lock. The number and percentage of subjects with major protocol deviations by deviation reason (e.g., nonadherence to trial drug, violation of select inclusion/exclusion criteria) will be summarized by treatment group that received in HZNP-HZN-825-301. A by-subject listing will be provided for all protocol deviations.

## **8.3 Demographic and Baseline Characteristics**

Descriptive summaries of demographic and baseline characteristics will be presented for the FAS and Safety Analysis Set. These characteristics include age, sex, race, ethnicity, height, weight, body mass index, region, and child-bearing potential (yes, no, not applicable). The use of mycophenolate mofetil (yes/no) and the presence of interstitial lung disease (ILD) (yes/no) based on a Screening HRCT scan will also be summarized, based on the values collected in the clinical database.

Systemic sclerosis history variables will include: time since SSc diagnosis (months), whether the patient has symptoms of SICCA syndrome, time with Raynaud's (months), time since first non-Raynaud's symptoms (months), diffusing capacity of the lungs for carbon monoxide (% predicted), incidence of subjects with gastrointestinal medical history (based on the SOC "gastrointestinal disorders"), incidence of the following symptoms: Raynaud's, digital ulcers, joint contractures, tendon friction rubs, and interstitial fibrosis (HRCT), as well as other related information collected. Systemic sclerosis history will be summarized by treatment group for the FAS.

Demographic data and Baseline characteristics will be provided in subject listings.

## **8.4 Prior and Concomitant Medications**

Prior and concomitant medications information will be collected in the database. Prior and concomitant medication verbatim terms in the eCRFs will be mapped to Anatomical Therapeutic Chemical (ATC) level 4 and preferred terms using the WHO Drug Global B3 Mar2021. Prior and concomitant medications will be summarized by presenting the counts and percentage of subjects using medications overall and by each treatment group based on Safety Analysis Set. Summaries will be provided by ATC Level 4 term and PT. Medication summaries will be sorted alphabetically by ATC Level 4 and by PT within ATC Level 4. Subjects will be counted only once for each medication class and each preferred drug name.

Prior and concomitant medications will be listed together with a designation to identify the medications as prior and/or concomitant and sorted by start date.

